Enter "Not Applicable" rather than leaving an item blank if the item does not apply to this project.

Version date: 9/30/2013

1. PROJECT TITLE

LinkUP: COVID-19 Intervention for underserved populations participating in parent study Proyecto La Frontera (UCSD IRB #191390).

3. FACILITIES

The UCSD investigators and staff for this project have offices on the main UCSD campus (La Jolla and [name] 'Webster Building').

The field operations for the evaluation component of this study will be carried out in part on the streets of San Diego County by UCSD's La Frontera staff. Operating on a mobile van, this component of the study will determine participant eligibility, obtain informed consent, refer consenting participants to our community partner (OnPoint), and conduct a prospective evaluation of the LinkUP intervention.

Sera are batched and delivered to Genalyte (San Diego, CA), a CLIA-certified lab that has obtained Emergency Use Authorization for their SARS-CoV-2 serology assay.

This project will be conducted in collaboration with a community partner, the Harm Reduction Coalition of San Diego (HRCSD) which operates a mobile Syringe Exchange Program (SSP) called OnPoint at 4 locations across San Diego. These 4 locations will be sites where participants will be offered rapid COVID19 antigen and/or SARS-CoV-2 PCR tests as part of their standard of care, and where participants will either receive the active version of the LinkUP intervention (education plus motivational interviewing) or the didactic version of the LinkUP intervention (control condition: education only). Both versions of the LinkUP intervention, as well as COVID testing, will be conducted by staff of OnPoint. Participants opting for SARS-CoV-2 PCR tests, or those testing positive on COVID rapid antigen tests will have their confirmatory PCR tests conducted by a certified lab of the California Department of Public Health (CDPH). Participants opting for vaccination will be referred participants for vaccine to nearby clinics. Because the HRCSD will be engaged in research activities such as administering the LinkUP intervention as part of this project, they will be reliant on UCSD which will serve as the IRB of record for this site, per NIH Single IRB mandate.

Data analysis for this study will be conducted by UCSD Staff at the Webster Building in Hillcrest. Analysis of de-identified data will also be conducted by the RADxUP Consortium Data Center at Duke University. LinkUP is a part of the RADxUP consortium, which is a network of U.S. research institutions supported by the US National Institutes of Health through the American Recovery Act. RADxUP aims to increase access to COVID19 testing and vaccination among marginalized communities across the US and is attempting to identify best practices based on information collected and shared across the consortium. The RADxUP Data Coordinating Center is based at Duke University in North Carolina

4. ESTIMATED DURATION OF THE STUDY

Two years: March 1 2021- August 30, 2023.

5. LAY LANGUAGE SUMMARY OR SYNOPSIS (no more than one paragraph)

Preliminary data from the parent study, La Frontera, have shown that people who inject drugs (PWID) in San Diego county are at high risk of COVID-19, yet have very low levels of COVID testing and vaccination. The goal of the present study is to evaluate a pilot intervention (LinkUP) to improve the uptake of COVID-19 testing and vaccination among PWID in San Diego County. Results will be shared with RADxUP consortium members, policymakers and program planners in California and across the US and used to estimate effect sizes for a future efficacy trial. Our study will inform efforts to leverage any of the 185 SSPs around the US as 'touchpoints' to reach marginalized communities, strengthening the nation's pandemic preparedness infrastructure to reduce COVID-19 health disparities.

6. SPECIFIC AIMS

Together with our community partner, the HRCSD's OnPoint, a mobile SSP, we will evaluate develop and evaluate an intervention to improve uptake of COVID-19 testing and vaccination. Our Study Aims are :

- 1) To adapt an existing behavioral intervention incorporating motivational interviewing (MI) to improve uptake of HIV pre-exposure prophylaxis among people who inject drugs (PWID), by replacing the educational content with information intended to improve uptake of COVID19 testing and COVID19 vaccination.
- 2) To pilot test the intervention in Aim 1 (called LinkUP) at OnPoint's 4 mobile SSP locations across San Diego County. We expect that the LinkUP intervention will be acceptable to PWID and considered feasible and sustainable by OnPoint staff and the project's Community Scientific Advisory Board (CSAB).

7. BACKGROUND AND SIGNIFICANCE

More than one year into the pandemic, SARS-CoV-2 is becoming endemic.[1] In the US, herd immunity against this virus is increasingly being considered unachievable due to vaccine hesitancy and new circulating escape variants.[2, 3] The implications are enormous: control over COVID-19 will only become possible with vaccine equity, which requires an infrastructure to offer COVID-19 testing, vaccination, boosters and health care to the most vulnerable communities. Understanding and overcoming barriers to COVID-19 testing and vaccination and developing interventions to improve their uptake is a critical public health priority.

COVID-19 Testing and Vaccination is Lagging Among PWID. California has done an admirable job of scaling up COVID-19 vaccination. However, like the rest of the country,[4] vaccine coverage is lower among under-represented minorities, especially Blacks and Latinx.[5, 6] To date, in the parent study (La Frontera), we have found that 36% tested seropositive for COVID-19 antibody. Of note, 32% had a COVID test before they joined our study, but 65% of those testing SARSCoV-2 seropositive had not been tested previously, indicating that the 'worried well' are those seeking testing, whereas the highest risk PWID are not.[7] Further, despite a robust vaccination program in San Diego County, only 9% of La Frontera participants had received a COVID vaccine as of Sept/21 and only 55% report they were willing to be vaccinated.[8] Further, we found that beliefs in COVID19 conspiracy theories and obtaining most of their COVID19 information from social media were independently associated with vaccine hesitancy.[8]

SSPs are undergoing expansion in CA and elsewhere. Research by our team and others consistently shows that syringe exchange programs (SSPs) attract PWID who are at higher risk of acquiring HIV and HCV,[9-12] representing a 'touchpoint' for those outside the health care system. SSPs are ideally positioned to offer ancillary services, such as referrals to substance abuse treatment, overdose prevention, testing for HIV, HCV, STIs and TB, as well as HBV vaccination and PrEP.[13] Mobile SSPs can reach the most vulnerable PWID who are homeless and lack transportation.[14] Across the US, states where SSPs can operate legally are more likely to offer these services, as well as medical care,[15] but their role in prevention, testing and vaccination for COVID-19 has been under-utilized.[16] 185 SSPs operating in the US have potential as venues to reach PWID at high risk of COVID-19.[16] The CDC and CDPH publicly endorse SSPs,[17, 18] and SD County's Supervisors recently embraced SSPs in 01/21.[19] In 2020, CDPH provided funding to 37 SSPs

across the state, including our lead community partner, the SD Harm Reduction Coalition's SSP, OnPoint. The CDPH are now offering free rapid COVID-19 and confirmatory PCR tests at SSPs across CA as well as free COVID-19 vaccinations. However, medical mistrust and vaccine hesitancy are anticipated to be persistent barriers, which our intervention will address. By basing our intervention at a SSP, we will create a potential model for pandemic preparedness that could be replicated at other SSPs to improve COVID testing and vaccination, which has been deemed a priority by NASTAD.[16]

This project is significant because PWID represent a medically and socially vulnerable population. High proportions of our study participants are ethnic minorities (75%), homeless (68%), have been in jail/prison (45%) or are HIV+ (6%). Our study team is uniquely poised to adapt and pilot an appropriate intervention in partnership with our established community partner, OnPoint, to encourage uptake of COVID19 testing and vaccination among PWID. Our prospective parent study, La Frontera, offers a mechanism to follow-up outcomes among PWID who are co-enrolled in LinkUP and compare them to those who are not. If our LinkUP intervention is deemed feasible and acceptable, we plan to apply to the NIH for additional funding to test its efficacy in other SSP locations around the US.

8. PROGRESS REPORT

N/A

9. RESEARCH DESIGN AND METHODS

La Frontera Parent Study Infrastructure: The parent study, La Frontera (R01 DA049644; PI: [name]; UCSD IRB #191390) was funded by NIH on 04/1/20 and is collecting prospective survey data and serology for HIV, HCV and SARS-CoV-2 on 600 PWID in both San Diego and Tijuana through 2025. This sub-study (LinkUP) will focus only on 150 PWID living in San Diego County based on the following eligibility criteria. LinkUP is funded by NIH through the RADxUP consortium, through the American Recovery Act which was enacted by US Congress in response to the COVID-19 epidemic.

Eligibility criteria for LinkUP. PWID participating in La Frontera were aged 18 or older at their baseline visit in 2020-2021, reported living in San Diego County, and injecting drugs within the last month. All were recruited into La Frontera between October 2020 and September 2021. To be eligible for the LinkUP substudy, subjects must be enrolled in La Frontera, report not having ever been tested for COVID-19 outside of La Frontera, and report not having had any vaccinations against COVID-19. They must also have provided consent to release their medical records with the study team, and consent to share their de-identified data with the RADxUP Data Coordinating Center at Duke University. Information on eligibility will be obtained through participants' most recent interviewer-administered survey in La Frontera. Potentially eligible participants who indicated that they are interested in participating will be contacted by La Frontera staff beginning March 1, 2022, at which time their eligibility for the LinkUp study will be re-confirmed using a short interview (screener) to ensure that their eligibility concerning COVID-19 testing and vaccination has not changed.

Baseline Data Collection. La Frontera staff will obtain written informed consent in person from the first 150 eligible La Frontera participants, who will form the LinkUP study sample. Consent forms will be offered in both English and in Spanish by trained bilingual staff. The LinkUP consent form will include permission to share their de-identified data between the OnPoint SSP and our study team. LinkUP participants whose last La Frontera interview was more than 3 months ago will undergo a brief interviewer-administered survey that addresses their potential barriers to COVID-19 testing and vaccination (baseline LinkUP survey). Measures include beliefs and attitudes to COVID testing and vaccination as well as structural barriers (e.g., lack of transportation, homelessness); these measures are already approved by the IRB under the parent study (IRB #191390). Surveys will be conducted by La Frontera's interviewers using computer-assisted programmable interviewing (CAPI). Interviews are done under canopies outside La Frontera's mobile van with plexiglass partitions and PPE for both interviewer and participant, as we have done for the La Frontera parent study. Interviews will be offered in both Spanish and English by trained bilingual staff. Participants will also undergo venipuncture for SARS-Co-V-2 serology. Following centrifugation, sera are batched and delivered to Genalyte

(San Diego, CA), a CLIA-certified lab that has obtained Emergency Use Authorization for their SARS-CoV-2 Maverick® Multi-Antigen Serology Panel[20] and tests for IgM and IgG antibodies against 13 unique viral antigens. Sensitivity and specificity for detecting SARS-CoV-2 antibody is 96% and 98% respectively. Following the interview and blood draw, each of the 150 participants will be given a laminated coupon indicating the address of the closest OnPoint syringe exchange location and the program's schedule and encouraged to attend this location at their earliest convenience. All enrolled participants will be provided with \$20 to reimburse their time and the cost of transportation.

Cluster Randomization. The four OnPoint syringe exchange locations will be randomized to deliver either the active (intervention) or didactic (control) version of the LinkUP intervention. The randomization scheme will be developed using an algorithm by La Frontera's statistician. Approximately three months into enrollment, there will be a one-week 'washout' period, after which time the two original intervention syringe exchange sites will become control sites and the two original control sites will become intervention sites. This cluster randomization scheme will help ensure that no neighborhood in San Diego County is denied access to the LinkUP intervention. By the end of the study, 75 LinkUP participants will have been randomized to an intervention site and 75 will have been randomized to a control site.

Participant Intake and Out-take Data at OnPoint Locations. OnPoint peer counselors will confirm that their client is a LinkUP participant when they are presented with the laminated card that was provided by LinkUP staff. They will then conduct a short 5 minute interview with the participant to obtain information on their COVID testing and vaccination history, their health status and any of their harm reduction needs to facilitate any referrals. After their visit, the peer counselor will supplement this with the Out-take data, which includes whether or not the participant received the LinkUP intervention and COVID-19 test(s). The information obtained will be shared through record linkage between OnPoint and La Frontera to confirm the study outcomes. Following the intake interview, the participant will either receive the LinkUP active or didactic intervention depending on the randomized allocation of the SSP site.

LinkUP Active intervention. The LinkUP intervention will be adapted from an intervention developed by UCSD faculty member [name], who developed an intervention combining education, motivational interviewing (MI), problem-solving, and ongoing support from peer navigators to increase uptake of and adherence to HIV pre-exposure prophylaxis (PrEP) among PWID attending SSPs in Massachusetts.[21, 22] The content of [name] intervention will be replaced with content on COVID-19, including basic information on its biology and epidemiology, and the safety and efficacy of available COVID-19 vaccines. This information will be drawn from literature shared by our RADxUP consortium leaders and is based on that provided by the CDC. Through an open discussion with one of OnPoint's peer counselors who are trained in MI, the counselor will present evidence-based COVID-19 information, which will also address COVID-19 misinformation (e.g., that COVID is no worse than the flu), and COVID-19 disinformation (e.g., that COVID vaccines include a tracking device). Next, the counselor will attempt to identify the participant's concerns about COVID-19 and vaccination in an attempt to tip their decisional balance. For example, in in-depth interviews, some participants expressed interest in vaccine only because it protected their loved ones whereas participants who are older or who have co-morbidities like obesity, HIV or diabetes may be more willing to consider COVID-19 testing or vaccination if they realize they are at risk of more serious disease. This session will be designed to be completed within 45 minutes. The LinkUP intervention will be available in English and Spanish. Qualified bilingual, bicultural staff will translate and back translate the intervention materials into Spanish. See Table 1 below for more detailed information on the intervention.

LinkUP Control Condition (didactic intervention). Given the vulnerability of our population, we plan to offer a didactic version of the LinkUP intervention as the control condition. Like the active version of the intervention described above, the didactic component will be conducted by an OnPoint counselor. They will be instructed to answer any questions the participant may have but to not engage in MI counseling. The same educational materials used above will be used for this session and it will be completed within 45 minutes. See Table 1 below for more detailed information on the intervention.

Table 1. LinkUP Intervention Components and Example Strategies

Component	Examples of Specific Strategies	Mediators
(a) COVID-19 Testing & Vaccine Education*	
 • Learning about COVID-19 symptoms and testing • Debating and debunking local COVID-19 misinformation (e.g., vaccine myths) • Learning about COVID-19 vaccines (including efficacy, doses, booster Q&A) • Identifying where and how to obtain testing and vaccines 	Increased COVID-19 testing & vaccine knowledge
(b) Motivational Interviewing**	
 • Reviewing factors contributing to local SARS-CoV-2 transmission, presenting plausible scenarios, adding personal meaning incl. personally-relevant risks • Rating personal testing and vaccine motivation; discussing what could increase it • Discussing costs and benefits of testing and becoming fully vaccinated • Elaborating on personally-relevant advantages of testing and vaccines • Aligning COVID knowledge/risk perceptions with testing and vaccine behaviors 	Increased COVID-19 testing & vaccine interest & motivation
(c) Problem-Solving and Planning**	
 • Problem-solving around personally-relevant challenges (e.g., competing health or priorities, schedules, homelessness, and other social and structural challenges identified by participants in formative research or by stakeholders*) • Providing enactive mastery experiences (i.e., practicing new skills) • Role modeling effective discussions with peers and healthcare providers • Handling missed appointments and devising back-up plans 	Increased COVID-19 testing & vaccine self-efficacy & behavioral skills
(d) Ongoing Support**	
 • As-needed assistance with: (i) planning/scheduling testing and vaccine appointments, (ii) attending appointments (accompanying if desired); (iii) problem solving around new/persistent challenges identified by participant; (v) maintaining cues/reminders for appointments; (vi) obtaining referrals for other health and social services • Reinforcement (verbal encouragement) for making, following-through on plans • Future planning for ongoing testing and sustained vaccination (as needed and recommended, incl. boosters), developing systems for continued reminders, identifying external social supports 	Reduced structural barriers to testing & vaccination

*Given to all participants (i.e., both active and didactic LinkUP intervention arms).

**Given to only those participants assigned to a SSP site offering the active LinkUP intervention.

Both interventions will be offered in English or Spanish by trained bilingual staff.

COVID testing. The CDPH is now providing free rapid COVID-19 antigen tests (BiNaxNow®)[23] to SSPs across California, including OnPoint. This means that SSP clients can access free rapid COVID tests regardless of whether or not they are participants in the LinkUP study, as part of their standard of care.

After the participant receives either the active or didactic LinkUP intervention, the OnPoint peer counselor will offer the participant a rapid COVID antigen test, delivered on site at their SSP location. If the participant agrees to testing, it will be accompanied by brief pre- and post-test counseling according to the CDPH's training module, which is being offered to OnPoint staff in December 2021. BiNaxNow's rapid test is conducted on a nasal swab and provides results within 15 minutes. Those testing positive will be asked to provide a nasal swab for PCR confirmation at a CDPH certified lab. Participants who prefer to have a PCR test instead of a rapid test will be permitted to do so. Participants who receive PCR tests will be asked to provide their contact details to permit the counselor to contact them to receive their test results. Subjects testing positive on either or both tests will be advised to practice social distancing and when necessary, referred to available resources for homeless. Any participant testing positive or who has symptoms consistent with COVID-19 will be referred to the nearest community clinic for free medical care.

COVID-19 vaccination. The CDPH is providing free COVID-19 vaccines that have been FDA-approved (i.e., Pfizer, Moderna and Janssen) to SSPs across California. Upon completion of the intervention, OnPoint will refer participants for vaccine to nearby clinics.

Participant Reimbursement: LinkUP participants will be compensated \$10 for their visit at OnPoint regardless of whether or not they choose to undergo a COVID test or receive a COVID vaccine.

Outcome Ascertainment: COVID-19 Testing & Vaccination. Outcome ascertainment will involve record linkage between La Frontera and OnPoint to determine which participants visited the SSP site they were referred to, and if they received the LinkUP intervention and COVID19 tests. Since LinkUP participants who refused COVID-19 tests at the SSPs and will have obtained COVID19 vaccination elsewhere, we will obtain these data in three ways: 1) *Self-report from La Frontera follow-up interviews* conducted 6 months after randomization. 2) *Record linkage with the CDPH's COVID-19 database* based on electronic health records (EHRs) for participants who provided a release of medical information. Record linkage will confirm if and where COVID testing was done elsewhere, if COVID-19 vaccine was administered, type, dates and # of doses, as well as hospitalizations and deaths. 3) *Biological validation* of vaccination will also be done based on COVID-19 serology conducted by Genalyte, which is being conducted as part of their follow-up visits in the parent study, La Frontera.

Analysis: Although the LinkUP trial is not powered to assess efficacy, we will conduct an intent-to-treat analysis following CONSORT guidelines[24] and register it at clinicaltrials.gov before enrolment. We will compare socio-demographics across the two study arms (intervention and control) to ensure balance, controlling for potential confounders and study location if there are significant differences. To obtain effect sizes and standard errors, percentages along with 95% CIs for those who a) had a COVID test within 6 months of the intervention and b) had \geq one COVID shot within 6 months of intervention, respectively, will be calculated for the two study arms. To obtain Risk Ratio estimates (intervention/control), we will use a logistic regression mixed model with a) had a COVID test; and b) had \geq 1 COVID shot within 6 months of intervention, respectively, as outcomes, considering intervention (active vs. didactic) as the primary fixed effect, potential covariates (e.g., age, gender, homelessness, income) and a random intercept for subject. We will also assess acceptability and feasibility of the LinkUP intervention among OnPoint investigators, staff, and clients through focus groups and CSAB meetings.

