12. INFORMED CONSENT

La Frontera staff will be responsible for obtaining informed consent. Eligible participants will be informed that in order to participate in the LinkUP study they need to provide consent for release of medical records with the study team, and consent to share their de-identified data with the RADxUP Data Coordinating Center at Duke University. In addition, the informed consent form will include information about the intervention and the equal probability to be assigned to either the motivational interviewing or didactic component of the intervention. The research staff who will be responsible for obtaining informed consent will assess whether the potential participant has understood the study and consent form by asking key questions (e.g., "How much time will this take you?"; "What are the possible benefits for you?"). Because it is possible that some of our participants may be cognitively impaired, or they may not initially understand the consent process, we will test all potential participants for their comprehension of critical points in the consent form. Errors will be corrected and these potential participants will then be asked if they need further clarification. If, after further attempts to clarify any misunderstandings, we determine that they may not fully comprehend the critical aspects of the study, they will not be enrolled. The field coordinator will also be available to answer any questions raised by a given participant. If a potential participant decides she or he does not wish to participate, his or her decision will be honored regardless of how well they comprehend the study information. A copy of the consent form without any identifiers will be offered to all participants. The consent form includes a description of the study, the telephone numbers of the PIs where participants can call or leave a message 24 hours a day if they have any questions or concerns.

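### Recruiters draw on a known list in no set order under a predictable site swap, and nothing conceals site version from them, so contact timing is an unprotected route to selection by arm

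*Combined protocol and SAP*

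**What the plan says.** Section 9 (Eligibility criteria for LinkUP) takes candidates from the parent study: "Information on eligibility will be obtained through participants' most recent interviewer-administered survey in La Frontera". Those who have expressed interest "will be contacted by La Frontera staff beginning March 1, 2022". Under Baseline Data Collection, consent is obtained "from the first 150 eligible La Frontera participants, who will form the LinkUP study sample". Neither Section 9 nor Section 11, which repeats the recruitment steps, gives an order of contact.

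In Section 9 each enrolled person receives "a laminated coupon indicating the address of the closest OnPoint syringe exchange location". Section 11 is looser and says only that the coupon names one of the four sites. The participant chooses when to attend, and no time limit is set.

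Under Cluster Randomization, the parent study's statistician develops the site allocation. About three months after enrolment starts, following a one-week washout, "the two original intervention syringe exchange sites will become control sites and the two original control sites will become intervention sites". The version a person receives follows the allocation of the site and is delivered after the intake interview at OnPoint. No section says whether La Frontera recruiters are kept unaware of which version a site is running. Section 12 says the consent form will describe "the equal probability to be assigned to either the motivational interviewing or didactic component of the intervention".

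The Analysis paragraph of Section 9 plans an intent-to-treat comparison. Arms are compared on socio-demographics, and confounders and study location are controlled only where the arms differ significantly. The covariates given as examples are income, age, gender and homelessness. Neither period nor attitude to vaccination is named.

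**The concern.** In a cluster design, recruiting individuals after the clusters have been allocated opens a route to selection bias. Here three features combine.

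- The candidates are known in advance, and the parent study already measures their beliefs about testing and vaccination.
- The swap is a complete reversal, so knowing the first allocation is knowing the second.
- Staff decide when to approach each person.

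The closest-site rule fixes where a person is sent but not when. A recruiter who knows the schedule could approach a receptive person while that person's own site is running the active version and leave a reluctant one until it is not.

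What is at stake is the effect estimate. Section 5 says the results will be used to size a future efficacy trial. Selection bias moves the estimate itself and is not reflected in its confidence interval.

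**Working it through.** **1. The plan's own figure.** The plan gives no power calculation. It states arms of 75 and 75, and 75 + 75 = 150 agrees with the planned sample.

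**2. Chance of the active version.** Two of four sites are active in each period, so there are 6 possible draws. Any given site is active in 3 of them before the swap and, by reversal, in the other 3 after it. For a fixed site and period, P(active) = 3/6 = 0.50 over the draw. Once the draw is made, it is 0 or 1 for that site and period. The probability therefore stays at 0.50 only if the site and date of contact are settled without reference to the draw.

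**3. Whether 75:75 is guaranteed.** Expected active count = sum over sites of 150 × (site share) × (fraction enrolled in that site's active period).
- If each site enrols half before and half after the swap, this is 150 × 0.5 = 75 under every draw. It is also 75 if all four sites enrol equally.
- With assumed site shares of 40, 30, 20 and 10% and 70% enrolled before the swap, the two largest sites starting active gives 150 × (0.70 × 0.70 + 0.30 × 0.30) = 87. The opposite draw gives 150 × (0.30 × 0.70 + 0.70 × 0.30) = 63.

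The stated split thus holds in expectation but not in every draw.

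**4. Bias if recruiters time contacts by arm.** With no true effect, false risk difference = (share willing in active − share willing in control) × (uptake in willing − uptake in unwilling). All uptakes and gaps below are assumptions. The only related figure in the protocol is that 55% of parent-study participants were willing to be vaccinated (Section 7).

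| Uptake, willing / unwilling | 10-point gap | 20-point gap | 40-point gap |
|---|---|---|---|
| 20% / 5% | 1.5 | 3.0 | 6.0 |
| 30% / 5% | 2.5 | 5.0 | 10.0 |
| 40% / 5% | 3.5 | 7.0 | 14.0 |
| 60% / 10% | 5.0 | 10.0 | 20.0 |

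Entries are percentage points; for example, 0.10 × (0.30 − 0.05) = 0.025. A simulation of 3,000 trials of 150 at 40% / 5% agreed with the formula to within about 0.2 points.

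**5. Bias if contact order ignores the arm.** In the same simulation, willingness differed by period but contact was unrelated to site version. The mean false difference was between −0.2 and 0.0 points, because both versions run in both periods. A single draw can still be unbalanced. With the unequal enrolment of step 3, 40% / 5% uptake and willingness falling from 67% before the swap to 27% after, the false difference ranges from −4.8 to +4.8 points by draw and averages zero.

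**6. Scale.** At 55% willing and 40% / 5% uptake, overall uptake is 0.55 × 0.40 + 0.45 × 0.05 = 0.2425. The simple 95% half-width for a difference is 1.96 × √(2 × 0.2425 × 0.7575 / 75) = 0.137, or 13.7 points before any allowance for clustering.

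**The case against.** The strongest reply is that bias needs several conditions the protocol does not state. Recruiters would have to know each site's current version, use stored attitude answers, and time contacts site by site. Recruitment is by La Frontera staff and delivery by a separate organisation (Section 3). The coupon is described as carrying an address and a timetable, not a version. In a population that is 68% homeless (Section 7), staff may have little real control over timing. All of this stands, and it is why the point is a risk rather than a finding of bias.

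Three stronger readings are tempting, and the documents do not support them.

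- **That the contact date decides the arm.** The version received depends on the site's allocation at the OnPoint visit, and someone contacted before the swap may attend after it. Contact date is the lever that staff hold, and an imprecise one. The plan does not say when the analysis arm is fixed.
- **That the equal chance promised at consent is not delivered.** Step 2 gives exactly 0.50 over the draw when timing is independent of it. That the value becomes 0 or 1 afterwards is true of any allocation list prepared in advance.
- **That unordered contact, or the early enrolment of easily reached people, biases the comparison by itself.** Step 5 shows that on average it does not.

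It can also be said that baseline comparison and adjustment offer some protection. They do so only in part: attitudes are measured but not listed for adjustment, and the trigger is a significant socio-demographic difference, which a gap in willingness need not produce. Finally, this is a pilot not powered for efficacy, and many of the biases in step 4 are below 13.7 points. That limits the consequence but does not remove it, since the estimate is meant to be carried forward.

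**Conclusion.** The point holds as an open risk of selection bias. The list is known, contact order is free, the swap is fully predictable, and no concealment of site version from recruiters is described. The planned adjustment does not close the route.

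The size cannot be read from the documents. It is 2.5 points for a 10-point gap in willingness and 5 points for a 20-point gap at an assumed 30% / 5% uptake, and 1.5 to 20 points over the wider assumptions tabulated. It is about zero on average if recruiters do not know, or do not act on, the site versions. The consent statement is accurate on the same condition. The change is worth making because it is cheap and protects the effect size intended for the next trial. Confidence is medium, because what the recruiters will know is not stated.

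**What to change.** 1. **Conceal.** State that La Frontera staff who contact, screen and consent will not be given the site-version schedule, including the direction of the swap.
2. **Randomise contact order.** Before first contact, have the statistician list potentially eligible people by closest OnPoint site and randomise the order within each list. Divide the planned 150, not the whole list, so that about half are approached before the swap and half after at each site. Replace anyone unreachable or ineligible with the next person on that list. This protects the comparison even if the versions become known at the van, gives each person approached an even chance in line with Section 12, and makes about 75 per arm hold under every draw (step 3). Bring the coupon wording of Section 11 into line with the closest-site rule of Section 9.
3. **Fix the arm.** Define the intent-to-treat arm as the version allocated to the coupon's site on the date the coupon is issued, whatever the visit date. Include site and period in the model regardless of baseline tests. Report how many people attended after the swap on a coupon issued before it.

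The cost is one random list and a limit on who sees the schedule. Opportunistic enrolment at the van is reduced, and some people listed later will be tested or vaccinated while waiting and become ineligible. People who attend across the swap are analysed in an arm whose version they did not receive, which dilutes the contrast. Effects shared by everyone in a site and period remain; random contact order does not remove them.
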